8.8.2 Analysis of secondary efficacy endpoint

Similar to the primary endpoint analysis, the incidence of urogenital GC infection will be described

using frequencies and percentages with the difference between treatment groups analysed using a Chi-Square test. Note: for a subject to be considered re-infected with GC any positive NAAT test during the treatment phase (visits 1-5) will constitute re-infection utilized. For a subject to be considered not re-infected, a subject with a negative NAAT at visits 1 & 5 with no positive NAATs in between is deemed not re-infected.

As a complementary analysis, tables will be created which also summarize re-infection by each scheduled visit.

GC infection information will be listed.

8.8.3 Analysis of exploratory endpoints

Exploratory endpoints include:

- Adherence with AMPHORA gel usage during study (see section 8.7 for more details).
- Sensitivity analyses of the primary and secondary endpoints will be performed for mITT population subjects with $\geq 20\%$, $\geq 40\%$, $\geq 60\%$, $\geq 80\%$, and 100% product use adherence (as determined via Method 1 & 2).
- Re-infection rate analysis with alternative definition of no re-infection
- Subject satisfaction, sexual satisfaction, Female Sexual Function Index and Sexual Function Questionnaire

The proportion of subjects who experience at least one CT infection during the study intervention period will be summarized by treatment group using the mITT populations and subject adherence rates. Treatment differences between AMPHORA and placebo will be tested by using Chi-square test (or Fisher Exact test, if necessary). A similar analysis will be conducted regarding GC infections. For the re-infection rate analysis with alternative definition of no re-infection, the primary & secondary endpoints will be analyzed as before with the exception that no re-infection will require negative NAAT results at Visits 1, 5 and at least 1 other schedule visit (i.e., Visits 2, 3, or 4). For satisfaction and sexual function questionnaires, descriptive statistics will be calculated for the AMPHORA group only. Listings will be provided with details for both treatment groups.

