| Subject Satisfaction with Product              |                      |   |                  |                  |                   | X                                  |  |
| Subject Sexual Satisfaction                    |                      |   |                  |                  |                   | X                                  |  |
| Female Sexual Function Index (FSFI)            |                      | X   |                  |                  |                   | X                                  |  |
| Sexual Function Questionnaire                  |                      | X   |                  |                  |                   | X                                  |  |

 Screening period may be up to 45 days. Subjects will be asked to return 7 days after Screening Visit. If subjects NAAT results are positive, they will be first treated by SOC then will return 3-4 weeks after Screening Visit (at least 21 days after treatment) for Enrollment/Visit 1. If the screening period extends past 45 days, subjects will not be enrolled and will need to be rescreened.

 Subjects must be asked to abstain from vaginal intercourse in the 24 hours preceding Study Visits 2 through 5.

Figure 1 **Schematic Flow of Study Design** 

 CT/GC NAAT testing is not required at this visit if subject was discontinued due to positive NAAT. For early termination, procedures for V5 should be followed with CT/GC NAAT testing required.

<sup>(4) Subjects will be asked to return  $\pm$  7 days within each visit window.

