#### 5.8.3 Enrollment/Visit 1 (Week $0 \pm 7$ days)

Subjects must be asked to abstain from vaginal intercourse in the 24 hours preceding Study Visit 1. The following will be recorded by research staff in the source documents and CRF:

- 1. Evaluation of inclusion and exclusion criteria
- 2. Evaluation of eligibility criteria
- 3. Demographic data
- 4. Completed Female Sexual Function Index (FSFI) and Sexual Function Questionnaire (SFQ)
- 5. Updated Medical/surgical/gynecologic/sexual history
- 6. Last menstrual period (date, if known)
- 7. Concomitant medication: all medications taken will be recorded in standard data collection forms with attention to drug route, daily dose, duration, start date, stop date and indications
- 8. Body height and weight
- 9. Vital sign measurements (blood pressure, heart rate, temperature)
- 10. Physical exam
- 11. Pregnancy test (urine)
- 12. Vaginal pH\*
- 13. Clinician-collected vaginal swab for CT and GC NAATs
- 14. Gynecologic examination\* (speculum, performed by clinician)
- 15. Randomization and issuance of study product (4-week supply based subject estimation of projected use)
- 16. Instructions on eDiary setup and use

Should subject be menstruating at time of scheduled visit, the visit may be rescheduled during the 7-day visit window, if possible.

Randomization, training, and verification of subject understanding, competency, and willingness to administer study product as directed is documented prior to issuance of study product.

If a subject's CT/GC NAAT results are positive at the enrollment visit, the subject should be immediately terminated from the study, IP accountability conducted, and all used/unused kits

\*Swab for vaginal pH reading is collected prior to introduction of speculum for gynecologic exam.

returned to the clinic. An Early Termination Visit should be performed to complete all procedures indicated for Visit 5 with the exception of repeat GC/CT NAAT testing. The subject should have SOC treatment for the infection and should be encouraged to return for a post-intervention follow-up visit approximately 4 weeks  $\pm 7$  days from Early Termination Visit or last

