#### 5.8.5 Visit 5 (Week $16 \pm 7$ days)

Subjects must be asked to abstain from vaginal intercourse in the 24 hours preceding Study Visit 5. The following will be performed, and research staff will record results in the source documents and CRF:

- 1. Changes in the following since last visit:
  - a. AEs
  - b. Concomitant medications
- 2. Pregnancy test (urine)
- 3. Self-collected vaginal swab for CT and GC NAATs
- 4. Targeted physical exam, as needed, based on symptoms
- 5. Subject diary review (sexual activity, product use since last visit)
- 6. Completed FSFI, SFQ, subject satisfaction with product, and subject sexual satisfaction questionnaires

7. Return of all unused study product and used applicators

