### 8.4.3 Analyses for Exploratory Objectives and Endpoints

Adherence with AMPHORA usage during study (rate of product use adherence) will be measured by inspection/analysis of returned gel applicators and eDiary data. Summary statistics of adherence overall and by intervention group will be provided.

Based on the adherence rate for each subject, sensitivity analyses will be conducted in the same manner as the primary and secondary endpoint analyses to examine if the level of re-infection between treatment groups differs for  $\geq 20\%$ ,  $\geq 40\%$ ,  $\geq 60\%$ , and 100% adherence rates. These sensitivity analyses will be performed on the mITT population.

Subject satisfaction with the study drug (including sexual satisfaction in **Appendix E**) will be summarized using frequency and percentage.

Subject sexual satisfaction will be measured utilizing baseline and follow-up questions on the impact of study drug on sexual function with the SFQ and item 10 on the FSFI. These scores and responses will be summarized using frequency and percentage.

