2.3 Exploratory objective

To determine if AMPHORA gel use rate (subject adherence to instructed use) has an effect on proportion of subjects who experience at least one CT or GC infection during the study intervention period.

To assess subject satisfaction (including sexual satisfaction) with AMPHORA gel over the course of the clinical trial.

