8 STATISTICAL METHODS

8.1 General statistical conventions

All statistical procedures will be completed using SAS version 9.4 or higher on the SAS Grid.

Unless otherwise stated, all statistical testing will be two-sided and will be performed using a significance (alpha) level of 0.05. Two-sided 95% confidence intervals (CI) will be provided when relevant.

For continuous variables, descriptive statistics will include the number of non-missing values, mean, standard deviation, median, minimum, and maximum. For categorical variables, descriptive statistics will include counts and percentages per category. All summaries will be presented by treatment group, unless otherwise specified.

Baseline values for all parameters will be the most recent value prior to administration of study product or speculum exam.

All subject data will be presented in individual subject data listings. Unless otherwise stated, unscheduled visit results will be included in date/time chronological order, within patient listings only. All listings will be sorted by investigational site, patient number, and visit. The treatment group (AMPHORA, Placebo) as well as patient's age and sex (if available) will be stated on each listing. With respect to study tables, the mITT population will be used for efficacy analyses; safety population will be used for safety analyses.

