8.7 Treatment adherence

Adherence with AMPHORA gel usage during study (rate of product use adherence) is defined using the gel applicators and e-diary data. Specifically, adherence will be determined using 2 methods. Method 1: adherence = # of times product is properly used as noted in the e-diary / # of coital events noted during the treatment phase in the e-diary. Method 2: adherence = # of times product is used as determined by Trypan Blue staining / # of coital events during the treatment phase noted in the e-diary. Summary statistics of adherence by method will be presented overall and by treatment group.

Study product adherence will be calculated as: $100 \times [\text{adherence ratio calculated via Method 1 (or 2)}]$. The maximum percentage of doses used will be 100%.

Study drug compliance, times of product use (determined via e-diary & dye staining), and times of coital event will be summarized by treatment group by the number of subjects (n), mean, std dev, std error, median, min, and max.

Study drug compliance will be summarized in categories “ $\geq 20\%$ ”, “ $\geq 40\%$ ”, “ $\geq 60\%$ ”, “ $\geq 80\%$ ”, and “100%” using frequency tables. For the purposes of the frequency table, each compliance group will be deemed mutually exclusive (e.g., compliance rate of 41% would be in the $\geq 40\%$ category only and would not be counted in the $\geq 20\%$ category).

Treatment compliance data will be listed.

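### SAP 8.8.3 summarises the sexual-function questionnaires for AMPHORA only, so the planned tables have no concurrent comparator for a shift between Visit 1 and Visit 5

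*SAP*

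**What the plan says.** SAP 8.8.3 groups four instruments together: product satisfaction, sexual satisfaction, FSFI and SFQ. For all four, "descriptive statistics will be calculated for the AMPHORA group only", and both arms are then covered by listings. No other SAP section plans a placebo summary of these forms.

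The forms are not restricted by arm when they are collected. Protocol 5.8.3 has FSFI and SFQ completed at Visit 1. Protocol 5.8.5 lists for Visit 5: "Completed FSFI, SFQ, subject satisfaction with product, and subject sexual satisfaction questionnaires". Protocol Table 1 agrees, and its footnote 3 extends the Visit 5 procedures to women who stop early: "For early termination, procedures for V5 should be followed with CT/GC NAAT testing required". Protocol 3.5 keeps subjects and investigators blinded throughout.

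Two statements of purpose matter. SAP 2.3 gives the exploratory objective: "To assess subject satisfaction (including sexual satisfaction) with AMPHORA gel over the course of the clinical trial". Protocol 8.4.3 sets out how satisfaction with sex is to be assessed, namely by "utilizing baseline and follow-up questions on the impact of study drug on sexual function with the SFQ and item 10 on the FSFI", and it asks for frequencies and percentages.

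The general rule in SAP 8.1 is: "All summaries will be presented by treatment group, unless otherwise specified".

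**The concern.** Protocol 8.4.3 describes a reading across two visits that attributes what is seen to the study drug. The SFQ (Appendix F) asks how often certain problems occurred in the past month, and the FSFI (Appendix G) asks about the past 4 weeks. The items shown do not mention the gel. Attribution to the product therefore has to come from the design, and the design supplies it through a concurrent, blinded, randomised arm. The planned table leaves that arm out.

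There is a reason within the trial to expect some change over time, although the documents give no figure for it and this is my inference. Women enter after a recent chlamydia or gonorrhoea infection. Those positive at screening enrol 3 to 4 weeks later, after treatment. Their Visit 1 recall period can overlap the infection or its treatment; the Visit 5 recall period, at about week 16, does not cover that episode. Answers could shift between visits in both arms whatever the gel does.

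At stake is how an exploratory table is interpreted. A reader of the study report could take an improvement or a worsening in the AMPHORA group as the product's doing, with no summary alongside to check it against.

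**Working it through.** The documents give no sample size, expected response or target difference for these questionnaires, so there is no planned figure to reproduce. The check is a comparison of the text, followed by simple algebra.

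**1. What each form can show**

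| Form | Visit 1 | Visit 5 | Items ask about the product? | Planned summary |
|---|---|---|---|---|
| SFQ (Appendix F) | yes | yes | no | AMPHORA only |
| FSFI (Appendix G) | yes | yes | no, in the items shown | AMPHORA only |
| Product satisfaction (Appendix D) | no | yes | yes | AMPHORA only |
| Sexual satisfaction (Appendix E) | no | yes | yes | AMPHORA only |

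Only SFQ and FSFI have a baseline and a follow-up, and these are the two instruments that Protocol 8.4.3 ties to the effect of the study drug. Appendices D and E ask directly about the product at a single visit, so no shift between visits arises.

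**2. What the one-arm table contains**

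Let T be the change over time that would occur without any gel, A the effect of AMPHORA, and P the effect of the placebo gel, taken as additive.

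- AMPHORA shift, Visit 1 to Visit 5 = T + A
- Placebo shift, Visit 1 to Visit 5 = T + P
- Difference between arms = (T + A) − (T + P) = A − P

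The planned table shows only T + A. A given shift fits equally well with T = 0 and a product effect of that size, or with A = 0 and a time change of that size.

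**3. What adding the placebo column gives**

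The difference between arms removes T, provided that T is the same on average in both arms. Randomisation supports this if the women who return Visit 5 forms remain comparable. The result is A − P, not A. The comparator is also a 5 g vaginal gel in an identical applicator, used in the same way (Protocol 4.1, 4.1.1, 4.1.6). Items such as dryness or pain on penetration could respond to any gel, and such shared effects cancel.

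**4. How much information is left out of the tables**

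Protocol 3.4 randomises 422 women per arm, 844 in total. The share with no questionnaire summary is up to 422 / 844 = 50%. It is an upper limit because not every woman will return a Visit 5 form.

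**5. Other exploratory summaries**

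Adherence in SAP 8.7 is shown by arm: "Summary statistics of adherence by method will be presented overall and by treatment group". Condom use in SAP 8.8.4 is also shown by treatment group. The questionnaires are the exception, and SAP 8.8.3 gives no reason for it.

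**The case against.** The case for leaving the text alone has real substance.

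- **The stated objective is met.** SAP 2.3 asks about satisfaction with AMPHORA, and a one-arm table answers that. This stands for Appendices D and E, where a placebo column adds context only. It does not cover the use of SFQ and FSFI that Protocol 8.4.3 describes.
- **The exception is allowed.** SAP 8.1 permits departures from display by arm, and 8.8.3 states one openly. A reader might infer that the SAP contradicts the protocol here. The documents do not support that: for these forms Protocol 8.4.3 names no arms, whereas for adherence it explicitly asks for a summary by group.
- **The comparison remains possible.** A reader might infer that the placebo comparison is lost. It is not. The answers are collected and listed, so the comparison is unplanned rather than impossible.
- **The placebo is not an untreated control.** A reader might infer that a placebo column would isolate the effect of using a gel from change over time. It would not; as shown above, it gives AMPHORA against placebo gel. This limits what the added column can say and should be stated beside the table.
- **No change analysis is named.** SAP 8.8.3 says only descriptive statistics, and the table templates are in a separate document. This is fair, but collecting the same forms at two visits and describing them as baseline and follow-up invites the reader to compare the visits.
- **Adherence and condom use are imperfect parallels.** Both are crossed with infection rates by arm elsewhere in the SAP and so need display by arm for another reason. I treat the parallel as supporting context only.

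**Conclusion.** The point holds for SFQ and FSFI. The planned summary has no concurrent comparator, and a shift between visits in the AMPHORA group cannot be read from it as an effect of the study drug. This follows from the text and needs no assumption about how large any change over time is; the documents give no such figure, so I put no number on the possible error. The measurable extent is that the answers of up to half the randomised women go unsummarised.

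What a by-arm table would add depends on the women returning Visit 5 forms being comparable between arms, and it is limited to AMPHORA against placebo gel.

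The importance is low. These are exploratory endpoints, the primary and secondary infection analyses do not use them, and SAP 8.9 and 8.9.1 already summarise adverse events by intervention group, including genitourinary events. A reader should not infer a weakness in the efficacy or safety conclusions from this point.

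**What to change.** In SAP 8.8.3, replace the restriction for SFQ and FSFI with wording along these lines:

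> For the SFQ and the FSFI item or items used, frequencies and percentages at Visit 1 and Visit 5 will be shown by treatment group. No statistical test will be performed.

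Add a footnote to those tables saying that the contrast is AMPHORA against placebo gel, so effects common to both gels, such as lubrication, are not shown.

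For the Appendix D and E forms, a placebo column is optional. If any AMPHORA-only display of SFQ or FSFI is kept, the SAP should give the reason and say that a shift between visits will not be interpreted as a product effect.

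The cost is slightly larger exploratory tables. No new data, visits or subjects are needed, because both arms' answers are already collected and due to be listed.

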8.8.4 Other Analysis

Condom usage rates and their effect on urogenital CT re-infection rates will be explored. The rate of condom usage will be defined as # of coital acts where male condom usage is noted in the e-diary (over the course of the treatment phase) / total # of coital acts during the treatment phase.

To assess the usage rate of condoms during the study, a summary will be presented using descriptive statistics for subjects displayed by treatment group. Additionally, a summary of re-infection rates by treatment group and condom usage (none, low, high) will be presented. For the purposes of this display, low condom use will be defined as subjects that have a rate that is less than or equal to the 50th percentile of subjects using condoms (i.e., no condom use will not be used for the 50th percentile calculation).

8.9 Safety analyses

All safety data will be summarized by intervention group. Safety analyses will be conducted on the Safety Analyses Set and will be performed for all safety variables specified below.

No statistical tests will be performed.

8.9.1 Adverse events

A summary of all adverse events that were reported will be presented by Medical Dictionary for Regulatory Activities® (MedDRA®-version 20.1 or higher) coding (System Organ Class and Preferred Term) by highest severity (one report by highest severity for each subject for that adverse event).

The incidence of adverse events (new or worsened) will be summarized by system organ class, preferred term, severity, and relationship to study intervention. The incidence of death, SAEs, and AEs leading to discontinuation will be summarized separately by system organ class and preferred term. Lastly, a summary of AEs by system organ class and relationship to study interventions will be provided.

An overall AE table will also be provided which provides a high-level of AE findings. As a part of this summary, subject & event counts for genitourinary events of FDA interest will be noted.

All adverse events will be listed.

8.9.2 Clinical laboratory evaluations

Specimens collected for NAATs will be processed by the sites and shipped to a central laboratory for testing. All other laboratory testing and staining of used applicators will be performed on-site.

Vaginal pH, NAATs for CT/GC, staining of used applicators, and urine β -human chorionic gonadotropin (uHCG) will be summarized by visit for each treatment group. Listings will be provided as well.

8.10 Interim analysis

There are no interim analyses planned.

9 ANALYSIS CHANGES FROM THE PROTOCOL

The following changes to the analysis plan have changed since the approval of the protocol:

- 1) Male condom usage summary statistics.
- 2) Assessing the effect of male condom usage on re-infection rates.
- 3) The data handling rules associated with subjects who enrolled multiple times in the study.
- 4) CT/GC re-infection rate sensitivity analysis
- 5) CT/GC re-infection rate summaries by timepoint
- 6) GU events summary added to the overall AE summary table
- 7) The mITT population has been relaxed to allow any randomized subject who uses product, whether or not there is coitus, and has negative CT/GC NAATs at baseline.

